9.1.1. Prior and Concurrent Illnesses and Medical Conditions

All current illnesses and past or pre-existing medical conditions will be coded using Medical Dictionary for Regulatory Activities (MedDRA) version 20.0 or higher.

Summaries of subjects’ prior and concurrent medical conditions will be presented by treatment group ([Table 27](#)).

Individual subject listings will be presented for all reported medical history including prior and concurrent medical conditions ([Listing 7](#)).

9.1.2. Prior and Concurrent Medications

Concomitant medications will be coded to the Anatomical Therapeutic Classification using the WHO Drug Dictionary. The use of concomitant medications during the study will be summarized by ATC1 and ATC2 code and treatment group for the Safety population ([Table 149](#)). A listing of concomitant medications will be presented ([Listing 17](#)).

9.2. Measurements of Treatment Compliance

All subjects are to receive IIV4 vaccine on Study Day 1. Subjects in Group 1 (Simultaneous Administration) will also receive the first dose of 2017 A/H7N9 in the contralateral arm on Study Day 1, with the second dose of 2017 A/H7N9 administered 21 days later (Study Day 22). Subjects in Group 2 will have two doses of 2017 A/H7N9 vaccine administered 21 days apart (Study Days 22 and 43). Subjects in Group 3 will receive no further doses. The number of study vaccinations administered to subjects will be presented by treatment group and by site in [Table 20](#), [Table 21](#), [Table 22](#), and as part of the subject disposition table ([Table 19](#)). [Listing 1](#) presents subjects who received investigational product with randomized treatment group and study product received for each vaccination.

9.3. Adverse Events

A summary of all adverse events is provided in [Table 100](#). A summary of those events that occurred in $\geq 5\%$ of subjects in any treatment group is provided in [Table 101](#).

9.3.1. Solicited Events and Symptoms

Systemic solicited adverse events were collected pre-vaccination, and systemic and local solicited adverse events were collected at-least 20 minutes post-vaccination and then daily for 7 days after each vaccination and graded on a scale of 0 (absent), 1 (mild), 2 (moderate) and 3 (severe). Systemic events include fever, feverishness, fatigue, malaise, myalgia, arthralgia, headache, and nausea. Local events include pruritus, ecchymosis, erythema, induration/swelling, pain, and tenderness. Ecchymosis, erythema, and induration are measured by both functional and measurement grading scales as defined in [Table 13](#). The grading scale for systemic events, including quantitative grading for fever, is included in [Table 14](#).

When calculating the incidence of solicited events, each subject will be counted once at the highest severity following the applicable vaccination, and any repetitions will be ignored. For summaries presented separately for each vaccination, the denominator for percentages will be the number of subjects who received the respective vaccination with non-missing data for the event summarized. For summaries over all vaccinations the denominator will be the number of subjects who received at least one vaccination with non-missing data for the event summarized.

The number and percentage of subjects reporting at least one solicited adverse event of each severity will be summarized for each solicited symptom, any systemic symptom, any local symptom, and any symptoms. For each event the denominator is the number of subjects who received the applicable vaccination with non-missing data for the specific event. The 95% CI calculated using Clopper-Pearson methodology from a binomial distribution (SAS Proc Freq with a binomial option) will be presented ([Table 102](#), [Table 103](#), [Table 104](#), [Table 105](#)). Logistic regression models will be fit to estimate the effect of treatment schedule on the

probability of reporting any local event or reporting any systemic event ([Table 106](#), [Table 107](#)). If statistically significant effects are observed in the model for local events or systemic events, then additional models will be fit for each individual event of that type.

$$\text{logit}[P(\text{Event})] = \beta_0 + \beta_1 \times \text{Treatment} + \varepsilon,$$

For each systemic and local event, any systemic event, any local event, and any solicited event, the maximum severity over 7 days after each vaccination will be summarized for the Safety population. The number and percentage of subjects reporting each event will be summarized by the maximum severity and treatment group, separately for each dose and over all doses. For each event the denominator is the number of subjects who received the applicable vaccination with non-missing data for the specific event. The 95% CI calculated using Clopper-Pearson methodology from a binomial distribution (SAS Proc Freq with a binomial option) will be presented ([Table 108](#), [Table 109](#), [Table 110](#), [Table 111](#)).

The number of subjects reporting a solicited adverse event will be summarized for each day post vaccination for each vaccination and for all vaccinations combined both in a summary table ([Table 112](#), [Table 113](#), [Table 114](#), [Table 115](#)) and graphically in a bar chart ([Figure 52](#) and [Figure 53](#)). A comparison of the event rate for each treatment group between study vaccinations will be presented for those groups receiving multiple vaccinations, including p-values from McNemar's test performed ([Table 116](#), [Table 117](#)).

Systemic and Local solicited events reported by subject will be presented in [Listing 10](#) and [Listing 11](#), sorted by subject ID, vaccination number, parameter, and study day.

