- Presence of signs or symptoms that could confound or confuse assessment of study vaccine reactogenicity. For subjects with injection site or systemic signs or symptoms, or with an acute illness, including an oral temperature greater than or equal to 100°F, the subsequent study vaccination should be postponed/deferred until signs, symptoms, or acute illness have resolved, or are improving as further specified below, and if within the acceptable protocol-specified window for Dose 2 (Group 1 and Group 2, Day 22+7), or Dose 3 (Group 2, Day 43+7). No exceptions to the protocol-specified window will be made. **Note for afebrile, acute illness only:** If a subject is afebrile, his/her acute illness is nearly resolved with only minor residual symptoms remaining, this occurs within the acceptable protocol-specified window for Dose 2 (Group 1 and Group 2, Day 22+7), or Dose 3 (Group 2, Day 43+7) and, in the opinion of the site principal investigator or appropriate sub-investigator, the residual symptoms will not interfere with the ability to assess safety parameters as required by the protocol, the subject may receive the subsequent study vaccination without further approval from the DMID Medical Officer. No exceptions to the protocol-specified window will be made.

- Grade 3 solicited or unsolicited AE that is ongoing, whether or not it is improved or resolving.
- Any unresolved or continuing Grade 2 AE that has not decreased in severity to Grade 1 or less.
- An unresolved or continuing Grade 1 AE is permissible following the documented determination by the site principal investigator or appropriate sub-investigator, that it would not render study vaccination unsafe or interfere with the evaluation of responses.
- Grade 3 solicited or unsolicited AE that occurs without alternative etiology in the 8 days following each study vaccination.

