Height and weight will be collected at the screening visit (optional) or on Day 1 prior to the first study vaccination for the calculation of BMI.

Reactogenicity assessments will include an assessment of solicited AEs occurring from the time of each study vaccination through Day 8 after each study vaccination, which includes an assessment of injection site reactions including pruritus (itching), ecchymosis (bruising),

erythema (redness), induration (hardness), edema (swelling), pain, and tenderness as well as systemic reactions including fever, feverishness (chills/shivering/sweating), fatigue (tiredness), malaise (general unwell feeling), myalgia (body aches/muscular pain exclusive of the injection site), arthralgia (joint pain exclusive of the injection site), headache, and nausea. Pre-administration reactogenicity assessments will be performed prior to each study vaccination to establish baseline, then the study vaccination will be given (see [Section 5.2.3](#)).

Subjects will be observed in the clinic for at least 20 minutes after each study vaccination. The study vaccination site will be examined, post-administration reactogenicity assessments will be performed, and any AE/SAEs will be recorded on the appropriate DCF prior to discharge from the clinic. The study vaccination site will also be examined approximately 7 days after each study vaccination.

All subjects will complete a subject memory aid from the time of each study vaccination through 7 days after each study vaccination. Subject memory aids will be reviewed with the subjects for AEs (solicited injection site and systemic reactions and unsolicited AEs) approximately 3 and 7 days after each study vaccination via phone call (Day 4) and clinical visit (Day 8).

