9.2 Methods and Timing for Assessing, Recording, and Analyzing Safety Parameters

9.2.1 Adverse Events

Adverse Event (AE): (ICH) E6 defines an AE as any untoward medical occurrence in a patient or clinical investigation subject administered a pharmaceutical product regardless of its causal relationship to the study treatment. An AE can therefore be any unfavorable and unintended sign (including an abnormal laboratory finding), symptom, or disease temporally associated with the use of a medicinal (investigational) product. The occurrence of an AE may come to the attention of study personnel during study visits and interviews of a study recipient presenting for medical care, or upon review by a study monitor.

AEs, including solicited injection site and systemic (subjective and quantitative) reactions, not meeting the protocol-defined criteria for SAEs will be captured on the appropriate DCF and eCRF. Information to be collected for unsolicited non-serious AEs includes event description, date of onset, licensed study clinician's assessment of severity and relationship to study product and alternate etiology (if not related to study product) (assessed only by those with the training and authority to make a diagnosis and listed on the Form FDA 1572 as the site principal investigator or sub-investigator), date of resolution of the event, seriousness, and outcome. AEs occurring during the trial collection and reporting period will be documented appropriately regardless of relationship. AEs will be followed through resolution.

Any medical condition that is present at the time that the subject is screened will be considered as baseline and not reported as an AE. However, if the severity of any pre-existing medical condition increases, it will be recorded as an AE.

AEs must be graded for severity and assessed for relationship to study product (see definitions below). AEs characterized as intermittent require documentation of onset and duration of each episode. The start and stop date of each reported AE will be recorded on the appropriate DCF and eCRF.

FDA defines an AE as any untoward medical occurrence associated with the use of a drug in humans, whether or not considered drug related.

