11.6.2 Safety Data

Summaries and analysis of safety data will be presented for the Safety Analysis Population. All summaries and analyses will be presented for all subjects.

Solicited AEs will be summarized by severity for each day after each study vaccination (Days 1-8 post each study vaccination) and as the maximum severity over all 8 days. Additionally, solicited AEs will be analyzed by taking the most severe response over the follow-up period, dichotomizing into a binary variable (none versus mild, moderate, or severe) and using standard techniques, such as exact confidence intervals, to summarize the proportion of subjects reporting each symptom, any injection site symptom, and any systemic symptom. Summaries of solicited AEs will be presented separately for each study vaccination as well as overall study vaccinations by treatment arm. The proportion of subjects reporting symptoms may be compared between

treatment arms using Chi-square or Fisher's exact test. The proportion of subjects reporting solicited symptoms between the different study vaccinations (i.e., first vs. second, first vs. third, second vs. third, as applicable within each study group) will be compared using McNemar's test.

Unsolicited AEs will be coded by Medical Dictionary for Regulatory Activities (MedDRA®) for preferred term and system organ class (SOC). The numbers of SAEs and MAAEs, including NOCMCs and PIMMCs, are likely to be small in this trial and will be reported by detailed listings showing the event description, MedDRA® preferred term and SOC, relevant dates (study vaccinations and AEs), severity, relatedness, and outcome for each event. Non-serious unsolicited AEs will be summarized as number and percentage of subjects reporting at least one event in each MedDRA® preferred term and SOC, cross tabulated by severity and relationship to study product. Additionally, the proportion of subjects and exact 95% CIs of AEs in aggregate and by MedDRA® categories will be computed.

Clinical laboratory data will be summarized by severity for each visit and as the maximum over all post-study vaccination visits. Graphical presentations may include box plots.

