Table 112: Number and Percentage of Subjects Experiencing Solicited Events by Symptom, Severity, Day Post Study Vaccination, and Treatment Arm (Safety Population) – Post Any Study Dose (continued)

Symptom	Severity	Pre-Dose		Post-Dose		Day 1		Day 2		Day 3		Day 4		Day 5		Day 6		Day 7		Day 8+		
		n	%	n	%	n	%	n	%	n	%	n	%	n	%	n	%	n	%	n	%	
Erythema (measurement)	None																					
	Mild																					
	Moderate																					
	Severe																					
Induration/Swelling	None																					
	Mild																					
	Moderate																					
	Severe																					
Induration/Swelling (measurement)	None																					
	Mild																					
	Moderate																					
	Severe																					
[repeat for all treatment groups]																						
N = Number of subjects in the Safety Analysis Population who received the specified dose. Severity is the maximum severity reported post dosing for each subject for each day.																						

Tables with similar format:

Table 113: Number and Percentage of Subjects Experiencing Solicited Events by Symptom, Severity, Day Post Dose, and Treatment Group (Safety Population) – Post Study Dose 1

Table 114: Number and Percentage of Subjects Experiencing Solicited Events by Symptom, Severity, Day Post Dose, and Treatment Group (Safety Population) – Post Study Dose 2

Table 115: Number and Percentage of Subjects Experiencing Solicited Events by Symptom, Severity, Day Post Dose, and Treatment Group (Safety Population) – Post Study Dose 3

Table 116: Comparison of the Number and Percentage of Subjects Experiencing Solicited Systemic Events by Dose and Treatment Group – Safety Population

		Subjects with No Symptoms	Subjects with Mild or Greater Symptoms	Total Number of Subjects n (Percent) [p-value*]
Study Dose 1 vs Study Dose 2				
Group 1: Simultaneous Administration (N=X)	Subjects with No Symptoms	x (%)	x (%)	x (%)
	Subjects with Mild or Greater Symptoms	x (%)	x (%)	x (%)
	Total Number of Subjects	x (%)	x (%)	x (100%) [0.xxx]
Group 2: Sequential Administration (N=X)	Subjects with No Symptoms	x (%)	x (%)	x (%)
	Subjects with Mild or Greater Symptoms	x (%)	x (%)	x (%)
	Total Number of Subjects	x (%)	x (%)	x (100%) [0.xxx]
Study Dose 1 vs Study Dose 3				
Group 2: Sequential Administration (N=X)	Subjects with No Symptoms	x (%)	x (%)	x (%)
	Subjects with Mild or Greater Symptoms	x (%)	x (%)	x (%)
	Total Number of Subjects	x (%)	x (%)	x (100%) [0.xxx]

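### A systemic symptom present at Grade 1 before a dose and unchanged after it counts as a solicited event, so a new-or-worsened count should be shown beside the planned one

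*SAP*

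**What the plan says.** Protocol 7.1 states: "Pre-administration reactogenicity assessments will be performed prior to each study vaccination to establish baseline". SAP 9.3.1 reports what this yields for analysis: "Systemic solicited adverse events were collected pre-vaccination". It mentions local symptoms only from the post-vaccination check onwards.

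SAP 9.3.1 then defines incidence: "each subject will be counted once at the highest severity following the applicable vaccination, and any repetitions will be ignored". Protocol 11.6.2 uses the same logic, taking the most severe response and "dichotomizing into a binary variable (none versus mild, moderate, or severe". The McNemar shell (SAP Table 116) sets its threshold at "Subjects with Mild or Greater Symptoms".

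The pre-dose grade appears in one place, the Pre-Dose column of the by-day shells (SAP Tables 112-115). It does not enter the rates with confidence intervals (Tables 102-105), the schedule models (Tables 106-107), the maximum-severity tables (Tables 108-111) or the between-dose comparisons (Tables 116-117).

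Protocol 5.2.3 foresees later doses in people who still have symptoms: "An unresolved or continuing Grade 1 AE is permissible following the documented determination by the site principal investigator". The sentence continues with a condition: the investigator must judge that the event would neither make vaccination unsafe nor interfere with evaluating responses. Minor residual symptoms of a nearly resolved acute illness are also tolerated, at entry (Protocol 5.1.2, footnote to criterion 1) and, in afebrile subjects, at later doses (5.2.3).

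**The concern.** The trial measures a baseline before every dose, but the headline analysis does not use it. Someone with mild fatigue or headache on arrival, and the same mild symptom that evening, is scored exactly like someone whose symptom began after the injection. Solicited events through 7 days are a primary safety outcome, so this affects the 'any' and 'mild' systemic rows, the model for any systemic event (Table 107) and the systemic McNemar tests (Table 116).

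The direction is known: a persisting symptom can add events and cannot remove them. At stake is how much of a reported systemic rate reflects the vaccine and how much is background. This matters most where true vaccine reactions are uncommon.

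**Working it through.** **The plan's own figure.** The only probabilities given for safety events are in Protocol Table 3 (SAP Table 8). With 1-(1-p)^n at n = 30, 60, 120:

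- p = 10%: 95.8, 99.8, 100.0
- p = 1%: 26.0, 45.3, 70.1
- p = 0.1%: 3.0, 5.8, 11.3
- p = 0.01%: 0.3, 0.6, 1.2

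Every cell agrees with the table, but none depends on the counting rule. The documents state no expected solicited-event rate and no pre-dose symptom prevalence.

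**Inputs.** From the documents: arms of 60, 60 and 30, and dosing occasions k = 2 (Group 1), 3 (Group 2) and 1 (Group 3). Assumed: e, the true new-onset probability per dose; b, the probability of a symptom present at dosing that persists unchanged (range 3% to 10%); independence of the two; the same b at each dose.

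**Per-dose excess.** Observed rate = e + (1-e)b, so the excess is (1-e)b, in percentage points:

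| e | b = 3% | b = 5% | b = 10% |
|---|---|---|---|
| 10% | 2.7 | 4.5 | 9.0 |
| 30% | 2.1 | 3.5 | 7.0 |
| 50% | 1.5 | 2.5 | 5.0 |
| 90% | 0.3 | 0.5 | 1.0 |

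**Against sampling error.** At e = 30%, n = 30: SE = sqrt(0.30 × 0.70/30) = 8.4 points, so the excess is 0.25, 0.42 and 0.84 SE. At e = 50%, n = 60: SE = sqrt(0.25/60) = 6.5 points, so the excess is 0.23, 0.39 and 0.77 SE.

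In general the excess is below one SE when b < sqrt(e/[(1-e)n]). That limit is 12.0% for e = 30%, n = 30; 12.9% for e = 50%, n = 60; 8.5% for e = 30%, n = 60; and 6.1% for e = 10%, n = 30. So at e = 10%, b = 10%, n = 30 the 9.0 points would exceed the SE of sqrt(0.10 × 0.90/30) = 5.5 points. A b of 10% is less plausible for a single symptom than for any systemic symptom.

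**After any dose.** With k occasions the excess is (1-e)^k × [1-(1-b)^k]. At b = 5%, in points:

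| e | k = 1 (Group 3) | k = 2 (Group 1) | k = 3 (Group 2) |
|---|---|---|---|
| 0% | 5.0 | 9.8 | 14.3 |
| 30% | 3.5 | 4.8 | 4.9 |
| 50% | 2.5 | 2.4 | 1.8 |

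The steep rise appears only if nobody truly reacts. At 30% it is nearly flat from two to three doses, and at 50% it falls.

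**Between arms (Table 107).** Assume e = 30% for an IIV4-only session and 60% for any session with H7N9. True any-dose rates are 30.0% (Group 3), 1 - 0.4² = 84.0% (Group 1) and 1 - 0.7 × 0.4² = 88.8% (Group 2). At b = 5% they become 33.5%, 85.6% and 90.4%. The odds ratio of Group 2 to Group 1 moves from 1.51 to 1.59, and that of Group 3 to Group 1 from 0.082 to 0.085. The shifts are small, and one is away from 1 while the other is towards it.

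**The case against.** The strongest case is that the rule is a deliberate, consistent and cautious convention. The endpoint is occurrence after each vaccination, not worsening, and both documents score it the same way. Protocol 2.3.1 says this H7N9 vaccine has not been evaluated in humans, so counting everything after dosing errs on the safe side. Requiring the post-dose grade to exceed the pre-dose grade would erase a true Grade 1 reaction in anyone who arrived with that symptom at Grade 1. This stands, and it is why the planned count should not be replaced.

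The eligibility rules also limit the problem. Protocol 5.2.3 defers later doses for symptoms that could confuse reactogenicity assessment and bars them while a Grade 2 event has not improved. Acute illness within 72 hours excludes at entry, subject to the allowance for minor residual symptoms. Fever is effectively ruled out: entry requires a temperature below 100.0°F, later doses are deferred at 100°F or above, and mild fever starts at 100.4°F. These rules shrink b without making it zero. The Pre-Dose column also shows background prevalence, but it cannot tell a reader which post-dose events were unchanged.

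Four stronger readings are tempting but unsupported:

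- **That the SAP departs from the protocol.** Protocol 11.6.2 has the same rule.
- **That the protocol already demands a worsening rule.** The sentence "if the severity of any pre-existing medical condition increases, it will be recorded as an AE" concerns medical conditions present at screening, not residual symptoms before a later dose.
- **That local rates are inflated too.** SAP 9.3.1 lists only systemic symptoms as collected before dosing. The Pre-Dose column in Table 112 runs across local rows, but that does not show the data exist.
- **That McNemar's test is distorted by carry-over.** Background symptoms raise both doses. Only persistence from one dose to the next would act differentially, and the documents give no evidence of it.

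**Conclusion.** The point holds for non-fever systemic symptoms. The stated rule counts an unchanged Grade 1 pre-dose symptom as a solicited event, and the baseline collected before each dose plays no part in the incidence tables, models or tests. The bias in the per-dose 'any' and 'mild' systemic rates is upward by (1-e)b.

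Its size cannot be derived from the documents. Under the assumed b of 3% to 10%, it is 2.1 to 7.0 points at e = 30% with n = 30, and 1.5 to 5.0 points at e = 50% with n = 60, below one SE in both. It could exceed one SE where the true rate is low and b is near the top of the range. All of this rests on independence between background and new-onset symptoms.

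A reader might infer that false events pile up with the number of sessions and so bias Group 2 against Group 3. In percentage points that is not generally so: at b = 5% and e = 50% the any-dose excess is 2.5, 2.4 and 1.8 points for one, two and three sessions. Halting rules based on Grade 3 reactions are not touched by an unchanged Grade 1 symptom. This is a cheap improvement in interpretability, not a flaw that invalidates the safety analysis.

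**What to change.** Keep the all-post-dose count as the main, conservative tabulation. Add to SAP 9.3.1, with Protocol 11.6.2 aligned, a prespecified supplementary analysis that counts a systemic solicited event for a dose only when the highest post-dose grade exceeds that subject's pre-dose grade for the same symptom at that dose. Show it alongside the systemic rows of Tables 102-105, Table 107 and Table 116. State how a missing pre-dose grade is handled. Do not extend the rule to local symptoms unless a pre-dose local assessment is confirmed in the analysis data.

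The cost is one derived variable from data already collected, a few extra tables and a sentence in each document. The drawback is that the new-or-worsened count can miss a true Grade 1 reaction in a subject who had a Grade 1 symptom at dosing, which is why both counts should be shown.

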6. GENERAL STATISTICAL CONSIDERATIONS

6.1. General Principles

All continuous variables will be summarized using the following descriptive statistics: n (non-missing sample size), mean, standard deviation, median, maximum and minimum. The frequency and percentages (based on the non-missing sample size) of observed levels will be reported for all categorical measures. In general, all data will be listed, sorted by site, treatment and subject, and when appropriate by visit number within subject. All summary tables will be structured with a column for each treatment group in the following order:

- Group 1: Simultaneous Administration (D1: IIV4/H7N9; D22: H7N9)
- Group 2: Sequential Administration (D1: IIV4; D22: H7N9; D43: H7N9)
- Group 3: IIV4 Only (D1: IIV4)

All tables will be annotated with the total population size relevant to that table/treatment, including any missing observations.

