14.3.1.1 Solicited Adverse Events

Table 102: Number and Percentage of Subjects Experiencing Solicited Events with 95% Confidence Intervals by Symptom and Treatment Group (Safety Population) – Post Any Study Dose*

Symptom	Group 1: Simultaneous Administration (N=X)		Group 2: Sequential Administration (N=X)		Group 3: HIV4 Only (N=X)	
	n	% (95% CI)	n	% (95% CI)	n	% (95% CI)
Any Symptom	x	xx (xx-xx)	x	xx (xx-xx)	x	xx (xx-xx)
Any Systemic Symptom						
Fever						
Feverishness						
Fatigue						
Malaise						
Myalgia						
Arthralgia						
Headache						
Nausea						
Any Local Symptom						
Pain						
Tenderness						
Pruritus						
Ecchymosis						
Ecchymosis (measurement)						
Erythema						
Erythema (measurement)						
Induration/Swelling						

Table 102: Number and Percentage of Subjects Experiencing Solicited Events with 95% Confidence Intervals by Symptom and Treatment Group (Safety Population) – Post Any Study Dose (continued)

Symptom	Group 1: Simultaneous Administration (N=X)		Group 2: Sequential Administration (N=X)		Group 3: HV4 Only (N=X)	
	n	% (95% CI)	n	% (95% CI)	n	% (95% CI)
Induration/Swelling (measurement)						
N = Number of subjects in the Safety Population who received any dose. 95% CI estimated using Clopper-Pearson exact method						

Tables with similar format:

Table 103: Number and Percentage of Subjects Experiencing Solicited Events with 95% Confidence Intervals by Symptom and Treatment Group (Safety Population) – Post Study Dose 1*

[Footnote update] N = Number of subjects in the Safety Population who received the first dose.

Table 104: Number and Percentage of Subjects Experiencing Solicited Events with 95% Confidence Intervals by Symptom and Treatment Group (Safety Population) – Post Study Dose 2*

[Footnote update] N = Number of subjects in the Safety Population who received the second dose.

Table 105: Number and Percentage of Subjects Experiencing Solicited Events with 95% Confidence Intervals by Symptom and Treatment Group (Safety Population) – Post Study Dose 3*

[Footnote update] N = Number of subjects in the Safety Population who received the third dose.

Table 106: Logistic Regression Model to Evaluate the Relationship of Treatment with Reporting Any Local Event Post Any Study Dose (Safety Population) *

Model Parameter	Parameter Category	Parameter Estimate	SE	p-value	Odds Ratio	95%CI
Intercept	N/A	xxx.x	xxx.x	x.xxx	-	-
Treatment	Simultaneous Administration (reference)	-	-	-	-	-

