	Sequential Administration	xxx.x	xxx.x	x.xxx	xx.x	xx.x-xx.x
	IIV4 Only	xxx.x	xxx.x	x.xxx	xx.x	xx.x-xx.x

N = number of subjects in the safety population.

Table with similar format:

Table 107: Logistic Regression Model to Evaluate the Relationship of Treatment with Reporting Any Systemic Event Post Any Study Dose (Safety Population) *

Table 108: Number and Percentage of Subjects Experiencing Solicited Events by Symptom, Maximum Severity and Treatment Group (Safety Population) – Post Any Study Dose*

Symptom	Severity	Group 1: Simultaneous Administration (N=X)		Group 2: Sequential Administration (N=X)		Group 3: IIV4 Only (N=X)	
		n	% (95% CI)	n	% (95% CI)	n	% (95% CI)
Any Symptom	None	x	xx (xx-xx)	x	xx (xx-xx)	x	xx (xx-xx)
	Mild						
	Moderate						
	Severe						
Any Systemic Symptom	None	x	xx (xx-xx)	x	xx (xx-xx)	x	xx (xx-xx)
	Mild						
	Moderate						
	Severe						
Fever	None						
	Mild						
	Moderate						
	Severe						
Feverishness	None						
	Mild						
	Moderate						
	Severe						
Fatigue	None						
	Mild						
	Moderate						
	Severe						
Malaise	None						
	Mild						

Table 108: Number and Percentage of Subjects Experiencing Solicited Events by Symptom, Maximum Severity and Treatment Arm (Safety Population) – Post Any Study Dose (continued)

Symptom	Severity	Group 1: Simultaneous Administration (N=X)		Group 2: Sequential Administration (N=X)		Group 3: HIV4 Only (N=X)	
		n	% (95% CI)	n	% (95% CI)	n	% (95% CI)
	Moderate						
	Severe						
Myalgia	None						
	Mild						
	Moderate						
	Severe						
Arthralgia	None						
	Mild						
	Moderate						
	Severe						
Headache	None						
	Mild						
	Moderate						
	Severe						
Nausea	None						
	Mild						
	Moderate						
	Severe						
Any Local Symptom	None						
	Mild						
	Moderate						
	Severe						

Table 108: Number and Percentage of Subjects Experiencing Solicited Events by Symptom, Maximum Severity and Treatment Arm (Safety Population) – Post Any Study Dose (continued)

Symptom	Severity	Group 1: Simultaneous Administration (N=X)		Group 2: Sequential Administration (N=X)		Group 3: HIV4 Only (N=X)	
		n	% (95% CI)	n	% (95% CI)	n	% (95% CI)
Pain	None						
	Mild						
	Moderate						
	Severe						
Tenderness	None						
	Mild						
	Moderate						
	Severe						
Pruritus	None						
	Mild						
	Moderate						
	Severe						
Ecchymosis	None						
	Mild						
	Moderate						
	Severe						
Ecchymosis (measurement)	None						
	Mild						
	Moderate						
	Severe						
Erythema	None						

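### The only between-group reactogenicity models (SAP Tables 106-107) pool events over all doses, so the schedule effect is mixed with the number of dosing sessions (2, 3, 1) and can be null, spurious or masked

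*SAP*

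**What the plan says.** SAP 9.3.1 plans logistic models with schedule as the explanatory variable; the outcome is the "probability of reporting any local event or reporting any systemic event". Treatment is the only term in the model. The section text gives no dose window. The Table 106 title does: "Reporting Any Local Event Post Any Study Dose". Table 107 does the same for systemic events. Both tables take Group 1 (simultaneous) as reference and carry coefficients for Group 2 (sequential) and Group 3 (IIV4 only).

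These two models also control what follows. The condition opens "If statistically significant effects are observed in the model for local events or systemic"; when it is met, per-symptom models of the same type (local or systemic) are added. The SAP does not say which coefficient counts or which dose window those models use.

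The rest of the plan on solicited events:

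- SAP 6.1 and Table 1 give two dosing sessions in Group 1 (IIV4 with H7N9, then H7N9), three in Group 2 (IIV4, H7N9, H7N9) and one in Group 3 (IIV4). Groups 1 and 2 receive the same three injections.
- Solicited events are collected for 7 days after each session.
- Tables 103-105 and 109-111 give percentages with exact intervals by dose number and group, with no model.
- The McNemar tests (Tables 116-117) compare doses within a group.
- Protocol 11.6.2 allows chi-square or Fisher tests between arms as an option and names no dose window.

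**The concern.** A subject with more sessions has more chances to report at least one event, and once a subject has reported one, later events add nothing to the outcome. The schedule coefficient therefore mixes two things: whether giving the vaccines together changes how people react, and how many separate sessions the schedule contains.

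Reactogenicity of sequential or simultaneous administration is part of the primary safety objective (SAP 3.1.1). Tables 106-107 are starred for the Preliminary Report, whose analyses count as final and may be published (SAP 6.2.1). A reader would naturally take the Group 1 v Group 2 odds ratio as the answer on co-administration.

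The per-dose tables do not supply the matched comparison directly. They are aligned by dose number, so the Dose 2 table puts Group 1's second H7N9 dose beside Group 2's first.

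**Working it through.** **Inputs from the documents.** Group sizes 60, 60 and 30 and an unadjusted alpha of 0.05 (SAP section 5); sessions per group (SAP 6.1). The two-sided likelihood ratio test is stated for the immunogenicity power tables and is assumed here for the safety models. All planned subjects are assumed to contribute.

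**Inputs assumed.** The documents give no reaction rate per session. Protocol 2.3.1 gives only a direction: AS03-adjuvanted vaccine produces more injection site reactions than a licensed seasonal vaccine. Write i for the rate after IIV4 alone, h for H7N9 alone and c for the co-administered session. The main illustration uses i = 0.4 and h = 0.6.

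**Check on the plan's own figures.** No figure is stated for Tables 106-107. SAP Table 8 uses the same at-least-one-event formula, 1-(1-p)^n. At p = 1% and n = 30, 60, 120 this gives 26.0, 45.3 and 70.1, against the stated 26, 45 and 70; all 12 cells agree. Exact enumeration of the likelihood ratio test with 50 per group gives power of 0.80 to 0.81 in all five rows of SAP Table 10.

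**Pooled outcome, sessions independent within subject**

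- Group 1: 1-(1-c)(1-h)
- Group 2: 1-(1-i)(1-h)^2 = 1-0.6×0.16 = 90.4%
- Group 3: i = 40%

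The matched column compares Group 1 Dose 1 (rate c) with Group 2 Dose 2 (rate h), as visits, 60 v 60. Rejection is exact, at the two-sided 5% level.

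| Co-administered session | Group 1 pooled | Group 2 pooled | OR, Group 2 v 1 | Pooled rejection | Matched rejection |
|---|---|---|---|---|---|
| c = 0.60, same as H7N9 alone | 84.0% | 90.4% | 1.79 | 20% | 5% |
| c = 0.76, independent: 1-0.6×0.4 | 90.4% | 90.4% | 1.00 | 6% | 48% |
| c = 0.80, slightly more than independent | 92.0% | 90.4% | 0.82 | 7% | 68% |
| c = 0.85 | 94.0% | 90.4% | 0.60 | 13% | 89% |

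In row 1 the extra IIV4 session in Group 2 creates the difference. In rows 2 and 3 the co-administered visit is clearly more reactogenic than an H7N9 visit, but most of the extra reactors would have reported something at another session anyway, so the pooled outcome barely moves.

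**Group 3.** With no interaction (c = 0.76), Group 3 v Group 1 is 40% v 90.4%. The test rejects more than 99% of the time, because Group 3 receives no H7N9.

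**Sensitivity of the spurious Group 2 excess**

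- Equal rates of 40% in every session: 64%, 78% and 40% in Groups 1, 2 and 3; OR Group 2 v 1 = 2.04, rejection 43%.
- The same case with a random intercept for subject on the logit scale: rejection 26% (SD 1) or 15% (SD 2).
- Row 1 with the same correlation: 11% (SD 1) or 7% (SD 2).
- Row 1 with h = 0.9 instead of 0.6, sessions independent: about 2%, a ceiling effect.

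**The case against.** A reader might infer that Tables 106-107 must show a schedule effect even when co-administration does nothing. The documents do not support that. Groups 1 and 2 receive the same three injections, with Group 1's first two in opposite arms. If each injection reacts as it would alone, the pooled probabilities are identical and the odds ratio is exactly 1. Row 1 requires that IIV4 adds no reactors when given with H7N9. The 43% figure further requires equal rates for seasonal and adjuvanted vaccine, which sits badly with protocol 2.3.1, and independence within subject.

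Total burden over the regimen is also a legitimate quantity, since the number of visits is part of a schedule. Per-dose percentages are reported whatever the models show, and the plan states that it tests no formal hypothesis.

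A further fair point is that a matched comparison of any local event would create its own artefact, because it sets two injected arms against one. With independent arms at 0.4 and 0.6, Group 1 Dose 1 v Group 2 Dose 2 is 76% v 60% (OR 2.1), and Day 1 is 76% v 40% (OR 4.75), with no interaction at all.

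All of this stands as a limit on the claim. It does not remove the problem: no specified between-group model separates schedule from number of sessions, and the descriptive tables and the optional test do not pre-specify the matched comparison.

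**Conclusion.** The point holds in a limited form. The pooled models estimate the chance of any reaction over the whole schedule. Read as an effect of giving the vaccines together or apart, the Group 1 v Group 2 coefficient can be null, can spuriously favour simultaneous dosing (OR 1.8, 20% rejection) or can miss an excess at the co-administered visit (80% v 60%: 7% pooled, 68% matched). Which of these applies turns on a reaction pattern that the documents do not give. The sizes rest on assumed session rates and independent sessions; correlation and high rates reduce the spurious excess.

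Two further inferences should be avoided. A visit-level difference such as 80% v 60% is not evidence of interaction: independence alone gives 76%. Nor does the gate necessarily keep the per-symptom models from being run. The SAP does not say which coefficient opens it, and the Group 3 coefficient alone would very probably do so, for a reason unrelated to co-administration. Either way, the gate does not track the question of interest.

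**What to change.** Keep Tables 106-107 and label them as total burden over the whole schedule. Add three pre-specified contrasts:

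1. First H7N9 dose: Group 1 Dose 1 v Group 2 Dose 2.
2. Second H7N9 dose: Group 1 Dose 2 v Group 2 Dose 3.
3. Day 1 IIV4: Group 1 v Groups 2 and 3 combined.

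For local events, compare the arm that received the same product: H7N9 arm with H7N9 arm, IIV4 arm with IIV4 arm. Listing 11 already matches product to arm for Group 1 Dose 1. For systemic events, compare by visit and describe the result as the reactogenicity of the co-administered visit, not as an interaction.

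Fit the per-symptom models on these contrasts, state their dose window, and do not make them conditional on the pooled p-value.

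The cost is a few more models and table shells on data already collected, and a few more unadjusted comparisons, consistent with the plan's stated position on multiplicity (SAP 6.8).
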